2.6.2. IFN- λ ELISpot

Peripheral blood mononuclear cells will also be used in IFN- γ ELISpot assays to determine the breadth of prostate cancer-specific T-cell responses (defined by number of peptide pools or individual peptides recognised). These data may be used to build immunologic models of the immune system. The total (sum over antigens) response for a participant at a given time point is calculated using the average results of the sample performed in triplicate (SFU/10⁶ PBMC) for each stimulation antigen (i.e., PSA, PAP, 5T4, STEAP1) and is directly provided by Barinthus Bio's Immunology laboratory. As with the ICS data, results for each stimulation antigen are background-subtracted by subtracting the DMSO average result from the stimulation antigen's average result and is also directly provided by Barinthus Bio's Immunology laboratory.

A participant will be considered to have a response if the background-subtracted average result is greater than the associated positivity threshold for each sample supplied by the Barinthus Bio immunology laboratory. Missing values will not be imputed for this analysis.

2.6.3. Other exploratory endpoints

Exploratory endpoints, including assessments of molecular markers (eg MSI-H, BRCA and expression level of VTP-850 antigens), ctDNA and PSMA scans, will not be analysed in this phase 1 part of the study.

2.7. Safety Variable(s)

The planned timepoints for all safety assessments are provided in Section 1.3 of the protocol. Vital signs will include temperature, systolic and diastolic blood pressure and pulse. Blood pressure and pulse will be measured in a sitting position after 3 minutes of rest. Vital signs will be measured at Screening, Days 1, 15, 29, 43, 57, 71, 91 and Months 6 and 24. Assessments at Days 57, 71, 91 and Month 6 may be repeated for participants receiving a third dose of MVA-PCAQ after initial PSA response followed by progression or in participants whose 2nd dose of MVA was delayed due to study pause.

A complete physical examination is performed at Screening only, and a symptom-directed physical examination will be performed at Days 1, 15, 29, 43, 57, 71 and 91 and Months 6 and 24/End of Trial visit. Assessments at days 57 and 71 may be repeated for participants receiving a third dose of MVA-PCAQ after initial PSA response followed by progression or in participants whose 2nd dose of MVA was delayed due to study pause.

Scheduled clinical laboratory assessments will be performed using a central laboratory at Screening, Days 1, 15, 29, 36, 43, 57, 64, 71, 91 and Month 6. Assessments at days 57, 64 and 71 may be repeated for participants receiving a third dose of MVA-PCAQ after initial PSA response followed by progression or in participants whose 2nd dose of MVA was delayed due to study pause.

Electrocardiograms (ECGs) will be performed at Screening, Days 1, 15, 29, 43, 57, 71, 91 and Month 6. Assessments at days 57 and 71 may be repeated for participants receiving a third dose of MVA-PCAQ after initial PSA response followed by progression or in participants whose 2nd dose of MVA was delayed due to study pause.

3.1. Estimands for the primary objective

The main estimand is defined through the following five attributes:

3.1.1. Treatment

The primary treatment is VTP-850 administered in three doses/regimens as follows:

Table 2: Phase 1 Trial Cohorts

Cohort		Number of Participants	Trial Intervention	
			ChAdOx1-PCAQ Day 1	MVA-PCAQ Days 29 and 57
1	IM/IM Low Dose	3-6	5×10^9 vp IM	5×10^7 pfu IM
2	IM/IM Full Dose	6	2.5×10^{10} vp IM	2×10^8 pfu IM
3	IM/IV Full Dose	6	2.5×10^{10} vp IM	2×10^7 pfu IV

IM=Intramuscular, IV=Intravenous, pfu=plaque forming units, vp=viral particles.

3.1.2. Population of Participants Targeted by the Clinical Question

The population targeted by the clinical question is defined through the inclusion and exclusion criteria as part of the clinical trial protocol version 5.

3.1.3. Variable Obtained from Each Participant Required to Address the Clinical Question

For each participant in the study, the variable to address the clinical question is the occurrence, grade, relationship to treatment and seriousness of adverse events from the start of the first VTP-850 administration continuing until the Month 6 visit.

3.1.4. Handling of Intercurrent Events to Reflect the Clinical Question of Interest

The following table describes how intercurrent events will be collected and handled within the analysis.

Table 3: Handling of Intercurrent Events for the Primary Estimand

Intercurrent event	Data collection and analysis
Start of new therapy, such as ADT	Participants will be followed and data collected prior to the occurrence of the intercurrent event in line with a while on treatment strategy.

3.1.5. Sensitivity Estimators for the Primary Estimand

Not Applicable.

3.1.6. Population-level Summary for Comparison between Treatment Conditions

The treatment effect will be quantified by the number and proportion of participants in each treatment group with adverse events, treatment-related adverse events, \geq Grade 3 AEs, \geq Grade 3 treatment-related AEs, serious adverse events and treatment-related serious adverse events. No formal hypothesis testing will be conducted.

4. Analysis Populations

In accordance with ICH E3 and E9³, the following analysis sets will be used for the analyses. The assignment of participants to the analysis sets (and whether any participant or specific data from a participant is excluded) will be determined at the pre-database-lock Data Review meeting.

4.1. All Screened Set

The All Screened Set will include every participant who has signed the informed consent form. The All Screened Set will be used for summaries of disposition and the associated listing.

4.2. Full Analysis Set

The Full Analysis Set (FAS) is based on the intent-to-treat principle and will consist of all participants who are enrolled into the trial and who received at least one dose of VTP-850. FAS participants are analysed according to the dose regimen that the participant was allocated.

The FAS will be used for summaries and analyses of efficacy endpoints that are not related to PSA.

4.3. Safety Analysis Set

The Safety Analysis Set (SAF) will consist of all participants who received at least one dose of VTP-850. SAF participants are analyzed according to the dose regimen the participant received.

The SAF will be used for summaries and analysis of demographics and baseline characteristics, treatments and medications, and primary safety endpoints including analyses of adverse events, laboratory safety tests and vital signs.

4.4. Efficacy Evaluable Set

The Efficacy Evaluable Set (EES) will consist of all participants in the FAS who had one baseline measurement of PSA and at least one post-baseline measurement of PSA. EES participants are analysed according to the dose regimen the participant was allocated.

The EES will be used for analyses of secondary efficacy endpoints which examine PSA response.

4.5. Per Protocol Set

Due to the small number of participants in the phase I part of this study, the Per Protocol Set (PPS), defined as participants in the FAS who received all planned doses of VTP-850 (Days 1, 29 and 57) at the protocol-defined dose and within the protocol-defined window (participants with delayed dosing due to study pause during the phase 1 portion of the trial as per protocol Section 6.12 will be considered to have dosing within the protocol-defined windows) and do not have any important protocol deviations leading to exclusion from the PPS. PPS participants are analyzed according to the dose regimen the participant received.

Protocol deviations are defined as any change, divergence, or departure from the study design or procedures defined in the study protocol. Important and non-important protocol deviations are referred to as major and minor protocol deviations, respectively, in the protocol. Important protocol deviations are a subset of protocol deviations that may significantly impact the correctness, accuracy, and / or reliability of the study data or that may significantly affect a participant's rights, safety, or well-being as outlined in the protocol deviation management plan and associated protocol deviation guidelines document. A full list of the important protocol deviations, and the subset that will lead to removal from the PPS, is described in the protocol deviation management plan. Important protocol deviations will be confirmed at review meetings before locking the clinical database.

4.6. Immunogenicity Analysis Set

The immunogenicity analysis set will consist of all participants who have available immunogenicity data at baseline and at least one post-baseline measurement and do not have any important protocol deviations that might impact the results of the immunological analysis as determined during population review meetings before database lock.

5. Data Handling

5.1. Time Points and Visit Windows

5.1.1. General Definitions

During the intervention period, assessment days are calculated relative to the date of the previous VTP-850 dose. During the screening, short-term and long-term follow-up periods, all assessment days will be relative to the first dose of treatment including assessments prior to the first dose of treatment.

During the screening, intervention, short-term and long-term follow-up periods, Day 1 is defined as the first dose of treatment except for the calculation of study windows described in Section 5.1.4 where, during the intervention period, day 1 will be defined relative to the first, second, third and optional fourth dose of VTP-850. Relative days after Day 1 are calculated as (assessment date – Day 1 date) + 1. Relative days prior to Day 1 are calculated as (assessment date – Day 1 date). The day prior to Day 1 is Day -1. There is no Day 0.

The date of the first dose of treatment for each participant will be taken from the ChAdOx1-PCAQ Administration eCRF page. The date of the last dose of treatment for each participant will be the latest date from the ChAdOx1-PCAQ administration or MVA-PCAQ administration eCRF pages.

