|--|--------------------------------------|----------------------------|----------------------|----------------------|---------------------|---------------------|-----------------------|---------------------|---------------------|----------------------------------|------------------------------------|----------------------------------|----------------------------------|---------------------|
| | | Day 1 Dosing Visit | Day 2 Telephone Call | Day 8 Telephone Call | Day 15 Clinic Visit | Day 29 Dosing Visit | Day 30 Telephone Call | Day 36 Clinic Visit | Day 43 Clinic Visit | Day 57 Dosing Visit ^b | Day 58 Telephone Call ^b | Day 64 Clinic Visit ^b | Day 71 Clinic Visit ^b | Day 91 Clinic Visit |
| Prior and concomitant medications | | <=====→ | | | | | | | | | | | | |
| Efficacy assessments | | | | | | | | | | | | | | |
| Serum PSA | X | X | | | | X | | | | X | | X | | X |
| Radiological assessment | X ⁱ | | | | | | | | | | | | | |
| Immunogenicity assessments | | | | | | | | | | | | | | |
| Blood for PBMC assessment ^j | | X | | | | X | | X | | X | | X | | X |
| Blood for ctDNA assessment | | X | | | | | | | | | | | | X |
| Blood for PSA-binding antibody/anti-vector antibody/anti-antigen antibody assessment | | X | | | X | X | | | X | X | | | X | X |

Abbreviations: AESI – Adverse Event of Special Interest, C3=Cohort 3, ChAd=ChAdOx1-PCAQ, CRP=C-reactive protein, CT=computed tomography, ctDNA=circulating tumour DNA, d=day(s), ECG=electrocardiogram, ECOG=Eastern Cooperative Oncology Group, MVA=MVA-PCAQ, MRI=magnetic resonance imaging, PBMC=peripheral blood mononuclear cells, PET=positron emission tomography, PSA=prostate-specific antigen, SAE=serious adverse event

^a If the screening period is longer than 42 days, the participant must be reconsented. Consult with the Medical Monitor for which assessments should be repeated.

^b Windows during the intervention period are calculated from the date of the previous VTP-850 dose.

^c If a cardiac event is reported, blood should be taken for an additional assessment of troponin T and the participant should undergo an additional ECG and echocardiogram at the earliest opportunity.

^d Historic echocardiogram may be used if performed within 3 months of Day 1.

^e May be retrieved at any time during the intervention period.

^f If troponin T test result is abnormal, a re-test on the following day is required.

^g Pre-dose and approximately 30 min post-dose.

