7.1 Discontinuation of Trial Intervention

It may be necessary for a participant to permanently discontinue trial intervention. Trial participants who present with at least one of the following VTP-850 discontinuation criteria listed below will be withdrawn from further trial intervention but will remain in the trial to be evaluated for safety, immunogenicity and efficacy, according to their PSA response and SoA ([Section 1.3](#)).

Ulceration, abscess or necrosis at the site of injection of trial VTP-850

Any CTCAE \geq Grade 3 AE considered related to VTP-850 and persisting continuously at \geq Grade 3 for >72 h, with the exception of Grade 3 laboratory test abnormalities that improve to Grade 1 or baseline grade within 14 days

- An SAE considered related to VTP-850
- Acute allergic reaction attributed to the administration of VTP-850

If the participant requests discontinuation of further dosing with VTP-850, it must be documented on the appropriate eCRF and in the medical records whether the participant is discontinuing also from trial procedures, post-intervention trial follow-up, and/or future collection of additional information.

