2.2.1.1. Endpoints for the Primary Objective(s)

- Number and proportion of participants with AEs, treatment-related AEs, \geq Grade 3 AEs, \geq Grade 3 treatment-related AEs, serious adverse events, and treatment-related serious adverse events
- Number and proportion of participants with clinically significant laboratory values
- Change from baseline for laboratory tests, electrocardiogram and vital sign measurements at each time point of collection

Full details for each endpoint are provided in Section 6.7.

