5.1.2. Screening Period

For all participants, the screening period is defined as the period from informed consent to the first administration of treatment. For some variables, such as data from scans, data are allowed prior to the date of informed consent provided the procedures met the protocol-specified criteria. For some variables, data from more than one assessment within the screening period can be collected prior to the first administration of treatment. The baseline value for a variable is defined as the last non-missing value collected before the first administration of treatment.

Assessments carried out on day of first administration of treatment are considered to have taken place before the first administration of treatment, except for vital signs recorded as post-dose and treatment-emergent AEs.

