Short-Term Follow-Up	Month 5	Day 150 ^a	Day 143 to 157 ^a	Day 136 to 165 ^a
Short-Term Follow-Up	Month 6	Day 180 ^a	Day 173 to 187 ^a	Day 166 to 195 ^a
Long-Term Follow-Up	Month 7	Day 210 ^a	Day 203 to 217 ^a	Day 196 to 225 ^a
Long-Term Follow-Up	Month 8	Day 240 ^a	Day 233 to 247 ^a	Day 226 to 255 ^a
Long-Term Follow-Up	Month 9	Day 270 ^a	Day 263 to 287 ^a	Day 256 to 285 ^a
Long-Term Follow-Up	Month 10	Day 300 ^a	Day 293 to 307 ^a	Day 286 to 315 ^a
Long-Term Follow-Up	Month 11	Day 330 ^a	Day 323 to 337 ^a	Day 316 to 345 ^a
Long-Term Follow-Up	Month 12	Day 360 ^a	Day 353 to 367 ^a	Day 346 to 400 ^a
Long-Term Follow-Up	Month 14	Day 420 ^a	Day 413 to 427 ^a	Day 401 to 440 ^a
Long-Term Follow-Up	Month 16	Day 480 ^a	Day 473 to 487 ^a	Day 441 to 509 ^a
Long-Term Follow-Up	Month 18	Day 540 ^a	Day 533 to 547 ^a	Day 510 to 569 ^a
Long-Term Follow-Up	Month 20	Day 600 ^a	Day 593 to 607 ^a	Day 570 to 629 ^a
Long-Term Follow-Up	Month 22	Day 660 ^a	Day 653 to 667 ^a	Day 630 to 689 ^a
Long-Term Follow-Up	Month 24	Day 720 ^a	Day 713 to 727 ^a	Day 690 to 749 ^a

^a Relative to first dose of treatment

^b Relative to second dose of treatment

^c Relative to third dose of treatment

^d Relative to optional fourth dose of treatment

Table 5: Definition of Visit Windows for Laboratory Assessments

Period	Visit	Target Day of Visit	Protocol Visit Windows	Analysis Visit Window
Screening	Screening	Day -1 ^a	Day -43 to -1 ^a	Not Applicable
Intervention	Baseline	Day 1 ^a	Day 1 ^a	Prior to or on Day 1 ^a
Intervention	Day 15	Day 15 ^a	Day 12 to 16 ^a	Day 11 to 27 ^a
Intervention	Day 29	Day 1 ^b	Day 1 ^b	Day 1 ^b
Intervention	Day 36	Day 8 ^b	Day 6 to 10 ^b	Day 2 to 11 ^b
Intervention	Day 43	Day 15 ^b	Day 12 to 16 ^b	Day 11 to 27 ^b
Intervention	Day 57	Day 1 ^c	Day 1 ^c	Day 1 ^c
Intervention	Day 64	Day 8 ^c	Day 6 to 10 ^c	Day 2 to 11 ^c
Intervention	Day 71	Day 15 ^c	Day 12 to 16 ^c	Day 11 to 27 ^c
Intervention	Additional Day 57	Day 1 ^d	Day 1 ^c	Day 1 ^c
Intervention	Additional Day 64	Day 8 ^d	Day 6 to 10 ^c	Day 2 to 11 ^c
Intervention	Additional Day 71	Day 15 ^d	Day 12 to 16 ^c	Day 11 to 27 ^c
Intervention	Day 91	Day 91 ^a	Day 89 to 91 ^a	Day 78 to 104 ^a
Short-Term Follow-Up	Month 6	Day 180 ^a	Day 173 to 187 ^a	Day 166 to 195 ^a

^a Relative to first dose of treatment

^b Relative to second dose of treatment

^c Relative to third dose of treatment

^d Relative to optional fourth dose of treatment

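### SAP visit windows for Days 29 to 71 need a boost date, so results of men who miss a boost can lack a by-visit timepoint; post-dose vital signs have no row of their own

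*SAP*

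**What the plan says.** The third primary safety endpoint in SAP 2.2.1.1 is "Change from baseline for laboratory tests, electrocardiogram and vital sign measurements at each time point of collection". PSA response is a secondary endpoint.

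SAP 5.1.1 opens with the rule "During the intervention period, assessment days are calculated relative to the date of the previous VTP-850 dose" and then, for the visit windows, sets the anchor: "during the intervention period, day 1 will be defined relative to the first, second, third and optional fourth dose of VTP-850". The footnotes to Tables 4 to 6 (PSA, laboratory, vital signs with symptom-directed examination) apply this. Rows for Days 29, 36 and 43 are "Relative to second dose of treatment", and rows for Days 57, 64 and 71 are "Relative to third dose of treatment". SAP 5.1.4 assigns a result to a visit only if its relative day lies within a window, boundaries included. Where several results share a window, the worst is used. The recorded eCRF visit name replaces windowing only for participants who have had a study pause.

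Under Protocol 7.1, a man who meets a discontinuation criterion "will be withdrawn from further trial intervention but will remain in the trial to be evaluated for safety, immunogenicity and efficacy", following the schedule of assessments. SAP 6.7.1 expects such men: it has exposure categories for the prime alone and for the prime with one boost.

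Protocol Table 1, footnote g, schedules dosing-day vital signs "Pre-dose and approximately 30 min post-dose". SAP 5.1.2 says that assessments on the first dosing day "are considered to have taken place before the first administration of treatment, except for vital signs recorded as post-dose", and SAP 5.1.3 places Day 1 post-dose data in the Intervention Period. In Table 6 the only row containing Day 1 is Baseline, whose window takes in everything up to and including Day 1.

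**The concern.** A window tied to a dose that was never given has no start date. The protocol still schedules the visit and the result is still collected, but the SAP has no rule that places it in a by-visit table. Missing a boost need not be random: the discontinuation criteria in Protocol 7.1 include persistent related Grade 3 events and acute allergic reactions. The by-timepoint laboratory and vital-sign summaries could then lack results from some of the men of most safety interest, while looking complete.

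The vital-sign rows raise a second question. The reading about 30 minutes after dosing is the one timed to show an acute reaction, including after the first-in-human prime, and Table 6 provides no row for it.

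**Working it through.** The plan states no figure for this, so there is none to reproduce. The check maps the scheduled visits onto Tables 4 to 6.

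**Inputs**
- Relative day = assessment date − anchor date + 1 (SAP 5.1.1).
- Windows anchored to the first dose: laboratory, Days 11–27, 78–104 and 166–195; vital signs, Days 11–27, 78–104 and 121–457; PSA, Days 78–104, 105–135, 136–165 and 166–195.
- Windows anchored to the second dose: Day 1 (all three tables); Days 2–11 (laboratory); Days 11–27 (laboratory, vital signs).
- Windows anchored to the third dose: Day 1 (all three); Days 2–11 (laboratory); Days 11–27 (laboratory, vital signs); Days 2–14 (PSA).
- Scheduled post-baseline visits to Month 6 (SAP 2.5 and 2.7): laboratory, Days 15, 29, 36, 43, 57, 64, 71, 91 and Month 6 = 9; vital signs, Days 15, 29, 43, 57, 71, 91 and Month 6 = 7; PSA, Days 29, 57, 64, 91 and Months 4, 5 and 6 = 7.
- Assumption: visits occur on their nominal days.

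**Control: fully dosed on Days 1, 29 and 57.** Day 36 is 36 − 29 + 1 = 8 and Day 43 is 15 from the second dose; Day 64 is 64 − 57 + 1 = 8 and Day 71 is 15 from the third. Every visit maps: 9 of 9, 7 of 7 and 7 of 7.

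**Prime only, no pause.** Only first-dose windows exist. For laboratory tests and vital signs they stop at Day 27 and resume at Day 78, leaving Days 28–77 uncovered. PSA has no post-baseline window before Day 78.

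**Second boost only missed, no pause.** Days 29 to 43 still map. Days 57, 64 and 71 have no third-dose anchor and precede Day 78.

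| Data | Prime only: visits without a timepoint | Second boost missed: visits without a timepoint |
|---|---|---|
| Laboratory | Days 29, 36, 43, 57, 64, 71 (6 of 9) | Days 57, 64, 71 (3 of 9) |
| Vital signs | Days 29, 43, 57, 71 (4 of 7) | Days 57, 71 (2 of 7) |
| PSA | Days 29, 57, 64 (3 of 7) | Days 57, 64 (2 of 7) |

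**Does the previous-dose wording help?** No. For a prime-only man the previous dose is the prime, and the gap is the same. For a man without the second boost, Days 57, 64 and 71 become 57 − 29 + 1 = 29, 36 and 43 after the second dose. The last second-dose window ends on Day 27 for laboratory tests and vital signs, and on Day 1 for PSA.

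**Dosing-day vital signs.** A Day 1 post-dose reading has relative day 1. Read literally, Table 6 puts it in Baseline, where it competes with the pre-dose value under the worst-value rule. That contradicts SAP 5.1.2 and 5.1.3. If Baseline is limited to pre-dose values to respect those sections, the reading has no row, because the next window opens on Day 11. On Days 29 and 57 both readings have relative day 1 from that dose and share one window. The worst-value rule does not say which of two unequal readings, both within range, is the worse.

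**The case against.** The strongest reply is that little safety information depends on these windows. They govern by-timepoint analyses only. Adverse event summaries, including those by administration, worst laboratory category and CTCAE grade, worst vital-sign change, any post-baseline potentially clinically important value, full listings and overall PSA response do not use them. That stands, and it rules out the inference that men with toxicity disappear from the safety analysis. The by-timepoint endpoint itself, however, is still not delivered for them.

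A reader might also infer that men stopped for a related SAE are the main loss. Protocol 4.1.6 pauses the trial for a related SAE or a related Grade 4 or 5 event, so the eCRF-name rule may cover them. The clearer gap is among stops that need not trigger a pause: persistent non-serious Grade 3 events, allergic or injection-site reactions, and participant choice.

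A third inference is that one such man is a large share of a column of 3 to 6. The documents do not support it. SAP 6.1 puts anyone without a second dose in IM/IM Full, men who do not complete dosing are generally replaced, and about 25 men are expected in Phase 1.

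Nor do Day 1 post-dose readings simply vanish. Read literally they have a row, but the wrong one, and SAP 5.1.3 makes them Intervention Period data that can count toward worst change. The table shells, which are not available here, may show pre- and post-dose rows. Shells set the layout, though; the assignment rule belongs in SAP 5.1.4.

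Finally, placing unboosted men in rows that otherwise hold post-boost values mixes exposures. That is a fair caution about the fix.

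**Conclusion.** The point holds in a limited form and should be corrected. Outside a study pause, the SAP gives no by-visit timepoint to scheduled Day 29–71 results of a prime-only man, or to Day 57–71 results of a man who misses only the second boost. The visit counts assume nominal visit days. Laboratory tests and vital signs are primary safety endpoints; PSA is secondary. How many men are affected cannot be derived from the documents, and how far the study-pause rule reaches depends on how it is read.

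For vital signs, the Table 6 structure applies to every participant: there is no separate post-dose timepoint on any dosing day, and on Day 1 the table conflicts with SAP 5.1.2 and 5.1.3.

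**What to change.** In SAP 5.1.4:

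- **Missed boosts.** Extend the existing eCRF-visit-name rule to participants whose second or third dose was not given, for PSA, laboratory and vital-sign data. Flag or footnote these values as unboosted so that they are not read as post-boost results. The small downside is mixed exposure within those rows, which the flag makes visible.
- **Dosing-day vital signs.** Split Table 6 into pre-dose and post-dose rows for Days 1, 29, 57 and Additional Day 57. Restrict Baseline to pre-dose readings and summarise change from baseline at each post-dose row.

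The cost is a short SAP amendment and a few extra table rows. No new data are needed: the visits and both readings are already scheduled, and SAP 5.1.3 already relies on the eCRF marking Day 1 data as post-dose.
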